In this study, we will evaluate the efficacy and safety of atorvastatin in SCD patients. At the completion of this trial, we will have an improved understanding of the contribution of endothelial dysfunction and soluble fms-like tyrosine kinase (sFLT-1) to the pathophysiology of albuminuria in SCD. If the data support the hypothesis that atorvastatin is safe and effective in this population, we plan on carrying out adequately powered studies to more definitively evaluate its safety and efficacy in the treatment and/or prevention of albuminuria in SCD.

Intervention: We will conduct a randomized, double-blind, placebo-controlled, crossover trial of atorvastatin (n = 19). Subjects will receive atorvastatin 40 mg/day or placebo for 6 weeks, separated by a 4 week washout phase. At the end of the washout period, a repeat history and examination and laboratory studies will be performed which will serve as a baseline for the second treatment phase, and patients will receive either atorvastatin or placebo, depending on their first treatment administration.

IND Holder: EXEMPT

Specific Aims:

- A) To evaluate the effect of atorvastatin on endothelial dysfunction, assessed using ultrasound imaging of the brachial artery, in sickle cell disease patients.
- B) To evaluate the effect of atorvastatin on plasma markers of endothelial activation, plasma levels of sFLT-1 and VEGF, heme oxygenase activity, rho/rho kinase activity, and TF-mediated sFLT-1 release from monocytes in sickle cell disease patients.
- C) To evaluate the effect of atorvastatin on albuminuria and estimated glomerular filtration rate in sickle cell disease patients
- D) To evaluate the association of endothelial dysfunction with pulmonary arterial pressure.

Hypotheses/Estimates: Our primary hypothesis is that endothelial dysfunction is an important contributor to the pathophysiology of albuminuria in SCD. We propose that atorvastatin will

Title of the Protocol: The effect of atorvastatin on endothelial dysfunction and albuminuria in sickle cell disease

improve endothelial dysfunction, decrease levels of sFLT-1, and decrease albuminuria in SCD patients.

Criteria for Evaluation:

Efficacy: Primary Endpoint: *Endothelial Dysfunction:* This will be assessed non-invasively using a brachial artery shear stress method. Assessments will be obtained at Baseline, and then at week 6 during the Treatment Phase. The primary efficacy measure will be a comparison of the % change in FMD from baseline to week 6.

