
Secondary Endpoints: *Endothelial Dysfunction:* The % change in NTMD from baseline to week 6 will be a secondary efficacy measure.

Endothelial Activation, sFLT-1, VEGF, heme oxygenase activity, rho/rho kinase activity and TF-mediated sFLT-1 release: We will measure plasma levels of soluble VCAM and soluble ICAM, plasma levels of sFLT-1 and VEGF; and assess heme oxygenase and rho/rho kinase activities at Baseline and then at week 6 during the Treatment Phase. Flow cytometry will be performed to assess monocyte activation state, absolute cell counts, TF expression, as well as TF-mediated sFLT-1 release from monocytes at baseline and at week 6.

Renal Function: We will assess the effect of atorvastatin on albuminuria (assessed by spot urine microalbumin/creatinine ratio) and estimated GFR at baseline and at week 6 during the Treatment Phase.

To examine the relationship of endothelial dysfunction, assessed using ultrasound imaging of the brachial artery, with tricuspid regurgitation velocity (TRV), Doppler echocardiography will be performed at baseline and at Week 6 in both treatment periods.

We will also evaluate patients for treatment-related complications by employing a history, physical examination, and routine laboratory tests (CBC, liver function tests, creatine kinase, lipid profile, and renal function). In addition to abnormal liver function tests and myopathy, we will monitor for episodes of SCD-related events.

Study Design: This is a randomized, double-blind, placebo-controlled, crossover trial of atorvastatin to evaluate the efficacy of atorvastatin in improving endothelial dysfunction and decreasing albuminuria in SCD. It will be divided into a screening/baseline phase, treatment phase, and follow-up phase.

Study Population: Nineteen patients with SCD (HbSS or HbS β^0 thalassemia) between the ages of 16 and 60 who meet the eligibility criteria and provide consent to participate in the study, will be randomized in this crossover trial.

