Endothelial Dysfunction – Vascular endothelial dysfunction will be assessed by measuring endothelium-dependent (flow-mediated) and endothelium-independent (nitroglycerin-mediated) dilation of the brachial artery as described previously (90,91). This technique has been safely performed in SCD patients (92,93). Subjects will be asked to hold all morning medications on days they have study visits until after the brachial ultrasound test. The reason for this is to avoid any effects of vasoactive medications. They are also required to refrain from smoking, vigorous exercise, caffeine, and eating and drinking (except water) for at least 6 hours before the brachial ultrasound procedure is scheduled. (Revised 06/03/2013.) Ultrasound images of the right brachial artery proximal to the antecubital fossa will be acquired using a 12 MHz linear-array transducer. The first set of baseline images will be obtained after 10 minutes of supine rest. Reactive hyperemia will be induced by inflating a pneumatic occlusion cuff placed around the upper forearm to a suprasystolic pressure (~ 200 mmHg) for 5 minutes, and then deflating the cuff. Images of the artery will be recorded for two minutes after cuff deflation. After 10 minutes of rest, a second set of baseline images will be acquired. Sublingual nitroglycerin (0.4 mg) will then be administered with acquisition of ultrasound images for the subsequent 5 minutes.

Gated end-diastolic images will be stored in a digital format on a personal computer for subsequent offline quantification. Each set of recordings will be coded and analyzed in random order by a blinded observer. Measurements will be performed using customized software (Brachial Tools, Medical Imaging Applications, LLC). Arterial diameter will be measured from the lumen-intimal interfaces of the proximal and distal arterial walls. Data from at least ten end-diastolic frames will be averaged for each baseline measurement and from at least three frames at maximum dilation during reactive hyperemia and following administration of nitroglycerin. FMD will be calculated as the % change in arterial diameter in response to reactive hyperemia, and NTMD will be quantified as the % diameter change following administration of nitroglycerin.

Assessments will be obtained at Baseline, Week 4 and Week 6 during each Treatment Phase. The primary efficacy measure will be a comparison of the % change in FMD from baseline to week 6. NTMD is a secondary efficacy measure.

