Endothelial Activation, sFLT-1, VEGF, heme oxygenase activity, rho/rho kinase activity and TF-mediated sFLT-1 release: We will measure plasma levels of soluble VCAM and soluble ICAM, plasma levels of sFLT-1 and VEGF (ELISA kits from R&D systems) and assess heme oxygenase and rho/rho kinase activities (see below) at baseline and then at week 6 of both treatment periods. Flow cytometry will be performed to assess monocyte activation state, absolute cell counts, TF expression, as well as TF-mediated sFLT-1 release from monocytes at baseline and at week 6.

Heme oxygenase activity: Heme oxygenase-1 (HO-1) protein in plasma will be determined (ELISA kit from Cusabio Biotech, Newark, DE) according to the manufacturer's directions. Tandem experiments will be performed using human microvascular endothelial cells (Lonza, Allendale, NY) to determine the ability of blood from SCD patients to induce HO-1 expression (94) and activity (95). **Rho/rho Kinase Activity:** The

activity of rho kinase will be assayed by western blotting with a phospho-specific and activation specific antibody (Anaspec) as previously described (96), in lysates prepared from the endothelial cells exposed to blood.

Renal Function – We will assess the effect of atorvastatin on albuminuria by spot urine microalbumin/creatinine ratio and estimated GFR at baseline, Week 4 and Week 6 of both treatment periods.

Safety – Subjects will be evaluated for safety throughout the study by history-taking, measurement of vital signs, physical examinations, and routine laboratory tests (CBCs, and chemistries including liver function tests, creatine kinase, lipid profile, and tests of renal function). In addition to abnormal liver function tests, myopathy, and other adverse events, we will monitor subjects for SCD-related events (Appendix 1).

Doppler echocardiography will be performed at baseline and at Week 6 in each study arm to examine the relationship of endothelial dysfunction, assessed using ultrasound imaging of the brachial artery, with tricuspid regurgitation velocity (TRV). (Added 06/04/2013.)

A hemoglobin analysis will be performed at screening to confirm diagnosis of sickle cell anemia (or HbS- β^0 thalassemia). (Added 08/26/2011.)

Statistical Methods: (revised 08/26/2011; revised 05/31/2013.)

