Statistical analysis strategy: Descriptive statistics of endothelial dysfunction measures (FMD%, NTMD%), soluble VCAM, soluble ICAM, sFLT-1, VEGF, heme oxygenase activity and rho/rho kinase activity will be presented by treatment and by visit, along with corresponding charts. FMD% and NTMD% will be log-transformed. To evaluate the effect of atorvastatin on endothelial dysfunction measures, we will perform a comparison of treatment by visit, using Student t-test subsequently followed by crossover ANOVA model testing carry-over effect and treatment effect. For soluble VCAM, soluble ICAM, sFLT-1, VEGF, heme oxygenase activity and rho/rho kinase activity, since they are not normally distributed, we will compare atorvastatin with placebo using Wilcoxon sign rank test. Similar analysis will be performed for the albuminuria and estimated GFR values. In addition, the relationship between outcome measures and treatment will be studied through a multiple regression analysis.

To evaluate the effect of atorvastatin on albuminuria, we will examine albuminuria both as a continuous variable using a linear mixed model to analyze the effect and as a categorical variable using a generalized estimating equation approach. Point estimates and confidence interval for the effect of albuminuria will be presented. Distribution of any complication among patients by treatment will be presented. The association of side effects by treatment will be tested using McNemar's test.

Differences in pre- and post- treatment echocardiographically-defined TRV will be described in tabular and graphical terms. (Added 06/04/2013.)

Sample Size Justification: Based on previous literature (70), we assume a standard deviation of 0.894 for changes in mean FMD%. In a 2x2 crossover design, the minimum required sample size is 9 per sequence to detect a clinically meaningful difference of 0.65 in mean changes in FMD% between atorvastatin and placebo groups at significance level $\alpha = 0.05$ with 80% power. Assuming a 5% attrition rate, we will enroll 19 patients for this study. (Revised 06/03/2013.)

Anticipated Outcomes: We anticipate that atorvastatin, by improving endothelial dysfunction, will decrease albuminuria in SCD. Furthermore, atorvastin will increase HO activity, but decrease rho kinase activity, sFLT-1 levels and TF-mediated sFLT-1 release from monocytes.

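### Does Aim D (endothelial dysfunction and pulmonary pressure) need its own prespecified analysis of FMD or NTMD against TRV?

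*Combined protocol and SAP*

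**What the plan says.** Specific Aims, item D, is an association aim: "To evaluate the association of endothelial dysfunction with pulmonary arterial pressure". The Assessments section gives the echocardiograms the same purpose: "Doppler echocardiography will be performed at baseline and at Week 6 in each study arm to examine the relationship of endothelial dysfunction", with TRV as the echocardiographic measure. The Secondary Endpoints in the synopsis agree.

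Statistical Methods mentions TRV once: "Differences in pre- and post- treatment echocardiographically-defined TRV will be described in tabular and graphical terms". That sentence and the echocardiography paragraph in Assessments carry the same addition date, 06/04/2013.

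The remaining methods in that section serve other questions:
- **t-test and crossover ANOVA:** the effect of atorvastatin on FMD% and NTMD%.
- **Wilcoxon test:** the biomarkers, with similar handling of albuminuria and estimated GFR.
- **Linear mixed model and GEE:** albuminuria.
- **McNemar's test:** side effects.
- **Multiple regression:** "the relationship between outcome measures and treatment will be studied through a multiple regression analysis".

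On timing, brachial ultrasound is covered by "Assessments will be obtained at Baseline, Week 4 and Week 6 during each Treatment Phase". Echocardiography is at baseline and Week 6, described as in both treatment periods (synopsis) or in each arm (Assessments). Potential Pitfalls calls the study exploratory.

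**The concern.** A before-and-after display of TRV cannot show whether TRV varies with FMD or NTMD. The nearest candidate, the multiple regression, has treatment as its explanatory variable and does not name TRV. Read strictly, one of four specific aims has data collection but no stated analysis.

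The worry is analytic freedom. Each patient contributes several echocardiograms, and nobody has said whether one pair per patient or all visits will be used, under which model, or what happens when a regurgitant jet cannot be measured. If those choices were made after seeing the data, and repeated visits were treated as independent, a chance correlation could be reported as a finding.

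**Working it through.** **1. The plan's own figure.** The sample size is built on FMD, not on Aim D. Inputs from Sample Size Justification: difference 0.65, SD 0.894, alpha 0.05, 80% power, 5% attrition. I take 0.894 as the SD of the within-patient treatment difference and a two-sided t-test with N - 2 degrees of freedom.
- 9 per sequence: noncentrality 0.65/(0.894/√18) = 3.09, df 16, power 82.5%.
- 8 per sequence: noncentrality 0.65/(0.894/√16) = 2.91, df 14, power 77.2%.
- Attrition: 18/0.95 = 18.9, so 19.

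The figure reproduces. Nothing in it depends on how TRV is analysed.

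**2. What Aim D can deliver with one pair per patient.** The documents give no expected FMD-TRV correlation. For illustration I use r = 0.33, the size of the sFLT-1/TRV correlation in Preliminary Data, which concerns a different pair of variables. Fisher z = atanh(0.33) = 0.3428, with standard error 1/√(n - 3).
- n = 18: 0.3428 ± 1.96/√15, back-transformed, gives -0.16 to 0.69.
- Correlation needed for 80% power: tanh(2.8016/√(n - 3)) = 0.62 at n = 18.
- If only 15 or 12 patients had a measurable jet (assumption; the documents give no share): 0.67 or 0.73.

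**3. Where the alarming numbers come from.** Assume four visits per patient, so 18 × 4 = 72 pairs. If these are treated as independent, 0.3428 ± 1.96/√69 gives 0.11 to 0.52, which excludes zero. If both measures share a within-patient correlation (ICC, assumed), the variance inflation under no association is 1 + 3·ICC², and the naive test's false-positive rate is 2[1 - Φ(1.96/√(1 + 3·ICC²))].

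| ICC | Inflation | Naive false-positive rate | Effective pairs, 72/inflation | 95% interval for r = 0.33, repetition allowed for |
|---|---|---|---|---|
| 0.3 | 1.27 | 8% | 56.7 | 0.08 to 0.54 |
| 0.5 | 1.75 | 14% | 41.1 | 0.03 to 0.58 |
| 0.7 | 2.47 | 21% | 29.1 | -0.04 to 0.62 |
| 0.8 | 2.92 | 25% | 24.7 | -0.08 to 0.64 |

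The false-positive column describes an analysis that the plan does not propose. The last column is the fair comparison with step 2. At ICC 0.7 to 0.8, where naive pooling is worst, a valid all-visits interval includes zero, as the one-pair interval does. At 0.3 to 0.5 it just excludes zero. So the choice between two valid analyses may matter at the margin, but only through an assumed ICC and a borrowed r.

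**4. The visit count is itself an assumption.** The echocardiography wording allows two baselines plus two Week 6 scans, or one baseline plus two Week 6 scans. The schedule of assessments has no echocardiography row to settle it. With three visits (54 pairs, inflation 1 + 2·ICC²) the naive interval is 0.07 to 0.55 and the naive false-positive rates are 7%, 11%, 16% and 19%.

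**The case for a change.** The strongest case for a change is that an exploratory label excuses low power but does not supply an analysis for a stated aim. The missing text would be a sentence or two, with no new data. The echocardiography purpose and the TRV analysis sentence were added on the same day and still do not match. Brachial ultrasound is also planned both at screening and at Day 0 of the first period, and the schedule lets these visits be merged without requiring it, so the first pairing is not strictly fixed. Preliminary Data restricts a TRV comparison to patients with a measurable jet, so missing values are foreseeable.

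The textual mismatch stands, and no other listed method closes it. The consequences are much weaker:
- **Error rate:** no TRV test is stated, so no stated test has an inflated error rate. The same section uses a mixed model and GEE for albuminuria, so the authors already turn to repeated-measures methods where visits recur.
- **Pairing:** the endothelial assessments are tied to the baseline of each treatment phase, which points to the Day 0 reading. What is left is a visit-window detail.
- **Log scale:** "FMD% and NTMD% will be log-transformed" is stated together with the treatment comparison. Values at or below zero are a separate matter and do not bear on a rank correlation.
- **Added text:** wording limited to FMD, or without hydroxyurea, would create new mismatches. The protocol counts NTMD as part of endothelial dysfunction, and Potential Pitfalls promises adjustment for hydroxyurea.

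**Conclusion.** No change to the plan is needed. This is missing detail on an exploratory secondary aim, not a rule that produces a wrong result. The TRV description is sound for what it covers, and the synopsis and Assessments already oblige the analysts to examine the relationship. An ordinary statistician would estimate a correlation with its interval from one pair per patient, report how many patients had a measurable jet, and use a patient random effect if all visits were included.

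The size is small. At 18 patients the interval around an illustrative r of 0.33 runs from about -0.16 to 0.69, so prespecification would not make Aim D confirmatory. The conclusion rests on 18 evaluable patients, on every TRV being measurable (fewer would widen the interval), and on analysts not treating repeated visits as independent, which nothing in the documents suggests they would do. A report that claimed an Aim D association from visits pooled as independent would deserve challenge, but that would be a fault in the report.
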